There were 3 groups 1) SIT: uninterrupted sitting (control); 2) LW: sitting + 3 min bouts of light-intensity walking at 3.2 km/h every 30 min; and 3) SRA: sitting + 3 min bouts of simple resistance activities (alternating half-squats, calf raises, brief gluteal contractions and knee raises) every 30 min (see below).

Simple Resistance Activities – SRA's

Over 22 h, both LW and SRA significantly reduced mean [interstitial] glucose, time in hyperglycemia and glycemic variability (quantified via the SD of mean glucose and mean amplitude of glycemic excursions) relative to uninterrupted sitting (Table). These simple interruptions to sitting significantly reduced the time in hyperglycemia, mean glucose and glycemic variability in adults with T2D. **This approach has not been studied yet in adolescents with type 1 diabetes.**

Table (A) Participant Characteristics and (B) Effects of the Three Trial Conditions on Glycemic Control

(A) Participant characteristics		(B) Effects of the three trial conditions on measures of glycemic control over 22 h			
Characteristic	N or mean (95% CI)	Measure of glycemic control	SIT (control)	LW	SRA
Number of study participants	14 M 10 F	Time in hyperglycemia (%)	60.3 (49.2, 71.3)	37.5 (26.5, 48.6)**	26.5 (15.5, 37.6)**
Age (yr)	62.3 (64.8, 59.8)	Time in hyperglycemia (hr)	13.3 (10.8, 15.7)	8.3 (5.8, 10.7)**	5.8 (3.4, 8.3)**
BMI (kg/m ²)	33 (34.4, 31.7)	Mean interstitial glucose (mg/dl)	11 (10.2, 11.8)	9.4 (8.5, 10.2)**	8.6 (7.8, 9.4)**
HbA1c (%)	7.2 (7.5, 7)	SD of mean interstitial glucose	2.2 (2, 2.5)	1.9 (1.7, 2.2)**	1.7 (1.5, 2)**
Note: All participants were Metformin/diet controlled individuals with type 2 diabetes.		MAGE (mg/dl)	104.94 (92.11, 117.78)	85.5 (72.66, 98.34)**	76.18 (63.35, 89.02)**
SD=standard deviation; MAGE=mean amplitude of glycemic excursions. *difference from SIT ($P < 0.05$); **difference from SIT ($P < 0.001$); Analysed using multi-level mixed models, controlling for age and BMI. Data are mean (95% CI).					

IV. Research Design and Methods

In this protocol we will determine whether 'exercise snacks', alone or in combination with dietary glutamine supplementation over a period of 3 months improve glycemic control in adolescents with type 1 diabetes.

Inclusion/Exclusion Criteria:

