Twenty-four adolescents with T1D for at least 12 months, between 13-19 yr-old will be recruited after informed written consent from their parents and the youngsters themselves. We will strive to recruit patients with comparable phenotype in both groups. They will be of normal weight (BMI between 10th and <85th percentile) and will be in puberty (at least Tanner stage III breast or genitalia) with a HbA1c between 7.5 and 9%. Subjects will be on either multiple daily injections (MDI) or insulin pump therapy. They will be recruited among the ~1,000 patients with T1D followed at Nemours Children's Clinic Jacksonville. We will exclude subjects with biopsy proven celiac disease, cystic fibrosis, chronic steroid therapy, mental retardation, microalbuminuria or evidence of other diabetic complications. Subjects involved in an active exercise program or in an organized sport team will be excluded. Studies will be conducted at least 2 weeks after resolution of any intercurrent infection.

Procedures: All subjects will have a full physical exam including Tanner staging as well as waist circumference measurement. A HbA1c, will be obtained as well as fasting triglycerides. A continuous glucose monitor (CGM iPro®, Medtronic Minimed, or a DexCom ^4) will be worn blindly for 6 days and data downloaded. Subjects will then be randomized to 2 study groups of 12 patients each:

(A) an 'exercise group', in which subjects will perform daily 'exercise snacks' within 30 min before breakfast, lunch, and/or dinner or bedtime snack, along with a placebo drink;

(B) an 'exercise + glutamine group', in which subjects will receive a glutamine drink (0.25 g/kg per dose) before meals TID, and perform 'exercise snacks' before each meal.

[figure not shown]
Allocation to the exercise only or the exercise + glutamine group will be stratified according to HbA1c range (eg, 7.5-7.9%; 8.0-8.4%; 8.5-9.0%), so as to ensure the comparability of groups.

The placebo and glutamine drink will be prepared at home using measuring spoons of glutamine or placebo powder to be mixed in a calorie-free, flavored soft drink tailored to the child's individual taste. Patients, families and investigators will be blinded as to the contents of the supplement.

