-Sample Size Justification: A sample size of 24 patients is planned assuming no more than 10% attrition rate. The main judgment criterion will be the mean amplitude of glycemic excursion (MAGE, measured using CGM). In the Australian study by Dunstan et al. [36]—described above in the Preliminary results section of this application—performed in adults with type 2 diabetes, MAGE was 104.9 ± 12.8 mg/dl (mean \pm SD) in the sedentary group of patients with type 2 diabetes, vs. 76.2 ± 12.8 mg/dl—i.e., a drop by 28.7—in the group performing short bouts of resistance exercise. To the best of our knowledge, there is no earlier study of such type of exercise in adolescents with T1D published in literature. Assuming ‘exercise snacks’ will decrease MAGE to the same extent in our population of children with T1D as in adults with T2D, such reduction will amount to an effect size of $\delta/\sigma=28.7/12.8 \approx 2.24$, where δ is the expected change in MAGE ($104.9-76.2=28.7$), and σ^2 the estimated variance of MAGE ($\sigma=12.8$, calculated based on [name] et al’s data). Using equations for unpaired studies, the number (n) of subjects per group needed to detect such difference with an α risk <0.05 , and a statistical power($1-\beta$) of 80% can be estimated as: $n= 2 \times (Z_\alpha + Z_\beta)^2 / (\delta^2/\sigma^2)$ [37], where $Z_\alpha=1.96$, and $Z_\beta=0.84$, therefore $n=2 \times (1.96 + 0.84)^2 / (2.24)^2 = 2 \times 7.84/5.02=3.1$. The enrolment of 12 patients per group therefore should be amply sufficient to test our hypothesis, even if we take into account a putative 25% attrition rate.

- Future Directions: These simple and short resistance activities as it was shown in previous studies [16, 36] have significantly reduced the time in hyperglycemia, mean glucose and glycemic variability in adults with T2D. With the ubiquity of sedentary behaviors and the low adherence to structured exercise, this approach has the potential to be beneficial and practical. This interesting approach has not been studied yet with combination of glutamine in patients with type 1 diabetes.

V. Facilities Required/Physical Location of Study

This study will be performed in outpatient settings and will recruit patients who are followed at the deivision of Endocrinology at the Nemours Children’s Healthy System in Jacksonville.

VI. References

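### The sample size treats a 95% CI half-width (12.8 mg/dl) as the SD of MAGE; with the SD that the interval implies, the plan's formula needs about 18–20 per group, not 3.1

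*Combined protocol and SAP*

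**What the plan says.** The Sample Size Justification in section IV makes MAGE from CGM the main criterion. It cites the interrupted-sitting study and states that "MAGE was 104.9 ± 12.8 mg/dl" in the sedentary condition and 76.2 with the same 12.8 under resistance activity, both labelled mean ± SD. "Using equations for unpaired studies", with two-sided α 0.05 and 80% power, it obtains an effect size of 2.24 and 3.1 subjects per group. It concludes that 12 per group is "amply sufficient to test our hypothesis, even if we take into account a putative 25% attrition rate".

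The source data are tabulated in section III(d), Table (B). The MAGE entries are "104.94 (92.11, 117.78" for sitting and "76.18 (63.35, 89.02" for resistance activity, and the footnote reads "Analysed using multi-level mixed models, controlling for age and BMI. Data are mean (95% CI". Table (A) lists 14 males and 10 females.

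**The concern.** The same 12.8 appears once as a standard deviation and once, in the source table, as the distance from a mean to its 95% confidence limit. A confidence limit describes the precision of a mean, and with 24 people it is much narrower than the spread between individuals. Entering it as σ inflates the effect size and shrinks the required n by the square of the error.

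The figure of 3.1 is the only numerical support for 12 per group on the main criterion. It suggests a margin of 12/3.1 = 3.9 times the need. A reader who relies on that margin could take a null comparison between arms as evidence of no effect when the study had limited ability to detect one.

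**Working it through.** **Inputs.** From the Sample Size Justification: δ = 104.9 − 76.2 = 28.7 mg/dl; σ = 12.8; Z values 1.96 and 0.84; 12 per group; attrition given as 10% in one sentence and 25% in another. From Table (A) and (B) in section III(d): N = 14 + 10 = 24, all contributing to each condition because the study is a crossover; MAGE limits 92.11 to 117.78 (sitting), 72.66 to 98.34 (walking), 63.35 to 89.02 (resistance).

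**1. Reproduce the plan's figure.** n = 2 × (1.96 + 0.84)² / (δ/σ)² = 2 × 7.84 / (28.7/12.8)² = 3.12. The stated 3.1 is reproduced, so the arithmetic is right for its inputs.

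**2. Identify the 12.8.** Half-widths: (117.78 − 92.11)/2 = 12.835; (98.34 − 72.66)/2 = 12.84; (89.02 − 63.35)/2 = 12.835. If 12.8 were the SD, the half-width with 24 people would be 1.96 × 12.8/√24 = 5.1, or 2.069 × 12.8/√24 = 5.4 using t with 23 df.

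**3. SD implied by the interval.** SD = half-width × √24 / critical value.
- Normal: 12.835 × √24 / 1.96 = 32.1.
- t, 23 df: 12.835 × √24 / 2.069 = 30.4.

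**4. Effect size and n by the plan's formula.**
- SD 30.4: d = 28.7/30.4 = 0.94; n = 15.68/0.94² = 17.6 (unrounded d).
- SD 32.1: d = 28.7/32.1 = 0.89; n = 19.6 (unrounded d).

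This is 18–20 per group, or 19–21 by t-test. Twelve is 12/19.6 = 0.61 to 12/17.6 = 0.68 of the requirement, before attrition.

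**5. Power and detectable difference** (two-sided t-test, unpaired, δ = 28.7 for power):

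| Per group | Power, SD 12.8 | Power, SD 30.4–32.1 | Detectable at 80% power, SD 30.4–32.1 |
|---|---|---|---|
| 12 | 99.9% | 55–60% | 36–38 mg/dl |
| 11 (about 10% lost) | 99.9% | 51–56% | 38–40 mg/dl |
| 9 (25% lost) | 99.4% | 43–47% | 43–45 mg/dl |

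**6. If change from baseline is analysed.** The Statistical Analysis section compares baseline with 3 months but gives no correlation r between them. Assuming r = 0.3–0.7 and δ = 28.7:
- Between arms, 12 per group, change score with SD × √(2(1 − r)): power 43–81%.
- Between arms, 12 per group, baseline-adjusted with SD × √(1 − r²): power 59–87%.
- Within subjects, exercise change, no concurrent control: 94% to >99% with all 24; 86% to >99% with 18 completers.

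**7. How far off the SD may be.** By the plan's formula, 12 per group suffices only if SD ≤ 28.7 × √(12/15.68) = 25.1, and 9 per group only if SD ≤ 28.7 × √(9/15.68) = 21.7.

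**The case against.** No reading of the table makes 12.8 a standard deviation. The serious objections concern what the corrected figures mean.

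- **Wrong contrast.** The 28.7 is resistance activity against sitting. Here one arm exercises "along with a placebo drink" and the other is the arm "in which subjects will receive a glutamine drink" as well as exercising, so no arm is sedentary. The 18–20 per group describes a comparison this trial does not make, and the contrast to which 28.7 does apply, the within-subject change with exercise, is well powered. This stands as a limit: the documents do not show that the trial is too small for that change. Equally, they offer no other calculation to support 12 per group for the randomised comparison.
- **Correlation.** The walking-versus-sitting MAGE difference, 104.94 − 85.5 = 19.44, is marked P < 0.001 in 24 people. That caps the SD of within-person differences at about 25–29 and suggests r of at least 0.55–0.69, so the lower change-score powers above may be pessimistic. But those conditions were about a week apart, and r over 3 months may be lower. Even at that cap, change-score power at 12 per group is guaranteed to be only about 64–76%, which is not ample.
- **Precision of the SD.** The 30.4–32.1 range reflects only the choice of z or t. Sampling error of an SD from 24 people gives about 24–45, hence n of about 11–39. The intervals are model-based, come from adults with type 2 diabetes, and cover 22 h per condition rather than 6 days of CGM. The SD must therefore be presented as approximate. None of this restores 12.8 or 3.1.

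**Conclusion.** The concern holds. The plan uses the half-width of a 95% confidence interval as the SD of its main criterion. Corrected with the study's own table, the effect size falls from 2.24 to about 0.9 and the same formula gives about 18–20 per group, roughly six times the stated 3.1. The sufficiency statement, with or without 25% attrition, does not follow.

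The mislabelling is certain. The size of the correction rests on an SD back-calculated from adjusted intervals in 24 adults with type 2 diabetes, and on the plan's own δ and unpaired comparison at a single time point. Power for glutamine versus placebo cannot be computed, because no expected glutamine effect on MAGE is given.

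**What to change.** Rewrite the Sample Size Justification paragraph:
- Replace σ = 12.8 with the SD implied by the interval, about 30–32 mg/dl, stated as approximate and with its source.
- Restate the effect size (about 0.9) and the n from the same formula (about 18–20 per group), and say that δ is exercise versus sitting.
- Delete the claim that 12 per group is ample. In its place give the power or detectable difference of 12 per group, about 36–38 mg/dl at 80% power for an unpaired comparison.
- Name the contrast to which the statement refers: glutamine versus placebo between arms, or within-subject change with exercise.
- Use one attrition rate and, if change from baseline is analysed, state the assumed correlation.

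The cost is one paragraph of text and less favourable stated figures. Correcting it does not in itself require more patients.

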-Calculations - An insulin sensitivity score (ISS) will be calculated as previously described using the SEARCH ISS model: $\log_e IS = 4.64725 - 0.02032(\text{waist, cm}) - 0.09779(\text{HbA1c, \%}) - 0.00235(\text{TG, mg/dl})$ ($R^2=0.74$ in the initial SEARCH model) [34-35]. This has been validated using the hyperinsulinemic euglycemic clamp, considered the gold standard for insulin sensitivity measures [34,35]. CGM data will be downloaded and used to calculate % blood glucose (BG) at, below or above target and the mean amplitude of glycemic excursions using a SAS program (MAGE) as previously described [17,21,22].

-Statistical Analysis and Statistical Power.

To determine whether short bouts of exercise and/or glutamine improve glycemic variability and diabetes control, we will compare the following parameters between baseline and 3 months:

- a) Changes in HbA1C
- b) Changes in MAGE
- c) Changes in % BG at target (70-180), below target (<70), above target (>180)
- d) Changes in ISS
- e) Changes in total insulin dosing (units/kg/day)

A mixed effects models and/or generalized estimating equations (GEE), which ever appropriate will be used within and between subjects and groups comparisons. Model assumptions will be checked by analyses. Significance will be established at $p<0.05$.

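### The sample size is worked out for exercise versus sitting, but both randomised arms exercise, so the glutamine-versus-placebo contrast has no sizing at all

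*Combined protocol and SAP*

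**What the plan says.** Under Procedures (section IV), 24 adolescents are randomised to two groups of 12. Group A does exercise snacks "along with a placebo drink". Group B takes glutamine "before meals TID, and perform 'exercise snacks' before each meal". There is no group without exercise.

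The Sample Size Justification names MAGE as the main criterion. It assumes that exercise snacks "will decrease MAGE to the same extent in our population of children with T1D as in adults with T2D", and takes δ = 104.9 − 76.2 = 28.7 mg/dl and σ = 12.8 mg/dl. The method is described as: "Using equations for unpaired studies, the number (n) of subjects per group needed to detect such difference". The result is 3.1 per group, followed by: "The enrolment of 12 patients per group therefore should be amply sufficient to test our hypothesis". That sentence allows for 25% attrition; the same paragraph opens with 10%.

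The Statistical Analysis section states the question as: "To determine whether short bouts of exercise and/or glutamine improve glycemic variability and diabetes control". It compares baseline with 3 months, within and between groups. The Specific Aims likewise ask about exercise with or without glutamine.

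**The concern.** An unpaired per-group formula sizes a comparison between two groups. The two groups here are exercise plus placebo and exercise plus glutamine. The δ entered is an exercise effect, from a study with no glutamine in any condition. For the randomised arms to differ by 28.7 mg/dl, glutamine would have to add a second effect as large as the whole assumed exercise effect, and the plan does not claim this. The glutamine pilot studies in section III report hypoglycaemia, plasma glutamine, blood glucose and clamp results, but not MAGE.

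This paragraph is the only sizing for the main criterion. Read as written, it would let a non-significant glutamine–placebo difference pass as the result of an amply powered trial, with no calculation behind that reading. Randomisation, HbA1c stratification and blinding all serve this contrast.

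**Working it through.** **1. The plan's own figure.** n = 2(1.96 + 0.84)² / (28.7/12.8)² = 2 × 7.84 / 5.03 = 3.1 per group. The arithmetic reproduces. It applies only to a 28.7 mg/dl difference between groups.

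**2. The SD.** The table in section III.d gives MAGE while sitting as 104.94 with limits 92.11 and 117.78, and its footnote says these are 95% confidence limits. Half-width = (117.78 − 92.11)/2 = 12.835, which is the figure the Sample Size Justification calls an SD. With 24 participants (14 M, 10 F), the implied SD is 12.835 × √24 / 2.069 = 30.4 (t, 23 df) or 12.835 × √24 / 1.96 = 32.1. This is approximate: the intervals are model-adjusted, from a 22-hour crossover in adults with type 2 diabetes.

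**3. Detectable glutamine–placebo difference** (two-sided 0.05, 80% power, noncentral t). The standardised difference is 1.197 at 12 per arm, 1.256 at 11 (12 × 0.90 = 10.8) and 1.407 at 9 (12 × 0.75). With baseline adjustment, multiply the SD by √(1 − ρ²) and drop one degree of freedom (1.200 at 12, 1.413 at 9). The baseline-to-3-month correlation ρ is not in the documents; 0.3–0.7 is assumed.

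| Analysis | n per arm | SD 12.8 | SD 30.4 | SD 32.1 |
|---|---|---|---|---|
| Unadjusted | 12 | 15.3 | 36.4 | 38.4 |
| Unadjusted | 11 | 16.1 | 38.2 | 40.3 |
| Unadjusted | 9 | 18.0 | 42.8 | 45.1 |
| Adjusted, ρ 0.3 | 12 | 14.6 | 34.8 | 36.7 |
| Adjusted, ρ 0.7 | 12 | 11.0 | 26.0 | 27.5 |
| Adjusted, ρ 0.3 | 9 | 17.3 | 41.0 | 43.2 |
| Adjusted, ρ 0.7 | 9 | 12.9 | 30.7 | 32.4 |

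Entries are in mg/dl. At 12 per arm, unadjusted, glutamine must add 15.3/28.7 = 53% of the assumed exercise effect even at the stated SD. At the implied SD it must add 36.4/28.7 = 127% or more.

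**4. Power for an illustrative add-on.** Assume glutamine adds half the exercise effect, 28.7/2 = 14.35 mg/dl. This is an assumption, not a figure from the plan.

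- Unadjusted, 12 per arm: 75% (SD 12.8) or 18–20% (SD 30–32).
- Unadjusted, 9 per arm: 61% or about 15%.
- Adjusted, ρ 0.3–0.7, 12 per arm: 78–96% or about 20–34%.
- Unadjusted n per arm for 80% power: 14, or 72–80.

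**5. The exercise change.** For a paired change the SD is σ√(2(1 − ρ)), so paired n = unpaired n × (1 − ρ). The unpaired n is therefore an upper bound for any ρ ≥ 0, and the formula itself does no harm here. What matters is the SD. Power for 28.7 mg/dl in arm A at n = 12 and SD 12.8 is above 99% even at ρ = 0. With SD 30–32:

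| n | ρ 0.3 | ρ 0.5 | ρ 0.7 |
|---|---|---|---|
| 12 | 67–71% | 81–85% | 95–97% |
| 9 | 51–56% | 65–70% | 86–89% |

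**The case against.** The strongest reply is that the hypothesis in question is the exercise effect, tested as change from baseline to 3 months. The sentence just before the calculation speaks only of exercise, δ is called an expected change, and the unpaired n is conservative for a paired test. Pooling both arms also raises power: with SD 30–32 and ρ 0.3, it is 94–96% at n = 24 and 86–89% at n = 18. This stands as a reading of the paragraph, and on it the trial is not short of patients for detecting a pre–post change. It does not rescue the paragraph. The Aims and the Statistical Analysis section make glutamine part of the question, and that part stays unsized. The pooled change mixes in any glutamine effect, and neither pooled nor single-arm change has a concurrent non-exercise control.

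It is also fair to say that the low power figures for glutamine depend on both an assumed effect and a replaced SD. At the plan's own SD, 12 per arm is close to enough for 14.35 mg/dl. Insufficiency therefore cannot be proved without a glutamine effect, and it is not claimed here. The powers also ignore the 1-month CGM, which a mixed model could use. Finally, a null result should be read mainly from its confidence interval; that supports reporting one, but does not support the adequacy statement.

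**Conclusion.** The concern holds. The arithmetic is right but belongs to a contrast that the trial does not randomise. The claim of ample size has no basis for glutamine versus placebo, because no effect on MAGE and no power are given for it. At 12 per arm and 80% power the unadjusted detectable difference is 15.3 mg/dl at the stated SD and about 36–38 mg/dl at the SD implied by the plan's own table; at 9 per arm it is 18.0 and 43–45. Baseline adjustment at ρ 0.3–0.7 brings the 12-per-arm figures to 11–15 and 26–37. That 12.8 is a confidence-interval half-width is firm. The SD of 30–32 is approximate, and the correlations and the 14.35 mg/dl increment are assumptions. For exercise, sample size is the lesser problem: no power figure makes an uncontrolled before–after change attributable to exercise.

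**What to change.** Replace the Sample Size Justification paragraph with three things.

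1. The detectable glutamine–placebo difference in MAGE change at 12 and at 9 per arm, using a corrected SD and a stated correlation range. With SD 30–32 and ρ 0.3–0.7, baseline-adjusted, that is 26–37 and 31–43 mg/dl. Either justify an effect of that size or present the contrast as an estimate with a 95% confidence interval. Labelling it exploratory is one way to do this.
2. Paired power for the pre–post change in arm A over the same SD and correlation range, with a sentence saying that without a concurrent non-exercise control the change cannot be attributed to exercise. If a pooled change is also intended, say so, and say that it includes any glutamine effect.
3. Removal of the statement that 12 per group is ample to test the hypothesis.

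The cost is one rewritten paragraph and a weaker stated claim. Enrolment and conduct stay as they are.
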